1) **Protocol Title:** Combining Lovastatin and a Parent-Implemented Language Intervention in a Multi-Modal Treatment of Fragile X Syndrome

2) Autl	nor of Protocol
XUC	C Davis Researcher
□ Re	searcher from other institution
□ Pr	ivate Sponsor
	operative Group
□ Ot	-

3) Objectives

Aim 1. Test the efficacy of a 20 week multi-modal treatment comprised of lovastatin and the Parent-implemented Language Intervention (PILI) for children with FXS. Children will be randomized to drug or placebo in a double-blind design with all participating in the PILI. The primary endpoint will be a spoken language composite and the secondary endpoint will be challenging behavior. We will test the following hypotheses:

Hypothesis 1a. Improvements in spoken language and behavior will be greater among lovastatin-treated than placebo treated participants.

Hypothesis 1b. Improvements in parental use of the PILI-targeted strategies will be associated with greater improvements in child language and behavior, especially in the lovastatin-treated group, thereby demonstrating benefit of the combined intervention.

Aim 2. (a) Identify biomarkers in peripheral immune cells associated with FXS and the efficacy of treatment and (b) elucidate the cellular/molecular mechanisms by which lovastatin influences MEK/ERK and Rho GTPase signaling pathways and immunological abnormalities associated with FXS.

Hypothesis 2a. Lovastatin corrects core biochemical and physiological impairments by normalizing Ca2+dependent and/or Ca2+-independent regulation of the MEK/ERK signaling pathway.

Hypothesis 2b. Lovastatin normalization of MEK/ERK signaling and/or Rho GTPase signaling is mediated by its effects on isoprenoid synthesis.

Hypothesis 2c. Individuals with elevated inflammatory cytokines will be more responsive to lovastatin.

4) Background

This is the first multi-modal treatment to combine a targeted treatment for FXS, lovastatin, with an innovative parent-implemented intervention (PILI) targeting language and challenging behavior delivered through telehealth technology. Our hypothesis is that targeted treatments will be more effective when applied in combination with PILI. We also will examine whether changes in the activity of key

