Once eligibility is confirmed, subjects will be approached to obtain their authorization to access and use their health information for the research. Please see Section 14 for additional information regarding Data Management and Confidentiality.

8) Compensation to the Subjects

Subjects will not be compensated for their participation. Possible expenses to the subject's family include time spent at the clinic as well as expenses for travelling. Therefore subjects who would otherwise not be able to participate may be eligible for travel reimbursement for travel costs incurred as specified in question 25.

9) Study Timelines

We anticipate seeing 30 pilot participants in the first 18 months under consent form C. During this same time period up to an additional thirty participants and their mothers will be seen under consent form A, phases 1 and 2 of the study. During Phase 3, 50 participants and their parent/caregiver will be recruited into the clinical trial portion utilizing consent form B. In addition, 3 subjects will be recruited into phase 4, under consent form D. Phases 2,3, and 4 of the study, using consent forms A, B and D, will occur over the last 3.5 years of the project).

10) Study Endpoints

The primary outcome measure is a spoken language composite measured at baseline and at the end of treatment. Comparison of the two treatment groups on the outcome measure will be made through analysis of covariance, adjusted for baseline values on that measure using an intent-to-treat approach. Two-sided tests will be used with alpha at .05. With this sample size, power to detect a moderate effect size of 0.6 will be 80%, assuming equal standard deviations in the groups. The assumptions we are making to estimate power are conservative as evidenced by recent published tests of a parent mediated intervention for autism (Rogers et al., 2012) and a randomized controlled trial of a drug in FXS (Berry-Kravis et al., 2012), with samples sizes of 98 and 60, respectively, and behavioral outcome measures.

Analysis of our secondary outcome measure, the social avoidance subscale of the FXS- normed ABC, as well as the exploratory VAS and CGI will follow the same approach as the primary analysis. Additional analyses will examine potential child moderators of response to lovastatin (age, Leiter, ADOS symptom severity) using linear regression.

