Aim 1. Hypothesis 1b. We will use linear regression to test the relationships between parent behaviors and child outcome at 20 weeks (i.e., spoken language composite). The regression will include main effect terms for both treatment and parent behavior as well as the interaction term, while controlling for baseline values of the parent and child measures. Various parent confounders will be

evaluated as well (e.g., SCL-90-R severity score). The main effect of the parent behavior will test the contribution of PILI, whereas the interaction term will test the value of the combined treatment. These analyses will be done separately with two parent behavior measures (parent verbal responsiveness composite and quality of caregiver involvement score).

Analyses will be repeated for secondary outcome measures.

Aim 2. In the addressing hypotheses 2a, b, and c, we will identify biomarkers associated with FXS using a regression model for marker expression with grouping of phenotype (i.e., disease state or respond to treatment) as a predictor with important clinical cofounders as covariates. The marker performance will be evaluated using receiver operating characteristic (ROC) curves to test which biomarkers are statistically better diagnostic and prognostic tests for FXS. We will further develop predictive signatures of elements involved in MEK/ERK and Rho GTPase signaling pathways in response to lovastatin using PAM, or other pattern recognized methods. The potential biomarkers are phosphorylation of S6K1, AKt, EIF4E, and ERK/MEK as well as levels of IL-1, IL-6, IL- 10, MCP-1, IL-1alpha, IL-1beta, MMP-9, and MIF.

Based on the findings of [name] et al. (2016, American Journal on Intellectual and Developmental Disabilities) statistical power for this study is expected to be sufficient with a subject enrollment of 50. In the [name] study, a treatment effect was demonstrated with the same outcome measure and same age range in a sample size of 10 per group. In this multimodal study, it is expected that the effect of the drug, if it is to be clinically meaningful, will be at last as large as the effect of the language intervention by itself in the 2016 study. In fact, the expectation is to see expect synergistic effects with the language intervention amplifying the effect of the drug.

11) Procedures Involved

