ix. Child Spoken Language: ICF A and B

The conversation and narration procedures described in Preliminary Studies will be administered at the baseline and post-treatment visits. Alternate versions of conversation and narration materials will be administered at the two visits and counterbalanced.

Neurobehavioral Analysis Core staff blind to hypotheses and participant characteristics will transcribe/code. A spoken language ability composite will be obtained for each assessment time by taking a weighted mean of variables reflecting talkativeness, fluency, intelligibility, vocabulary diversity, and syntactic complexity in combined narrative and conversational samples. This composite will provide a broad-based and robust measure of spoken language ability and serve as the primary outcome measure. Exploratory analyses will evaluate the separate contributions of the variables included in the composite (30 min).

DOS 5.1 (Version Date: 07-Nov-2017)

x. The Social Communication Questionnaire (SCQ): ICF D

A widely used informant report checklist that evaluates communication and social skill deficits common to those with symptoms of autism. This brief questionnaire will be completed by the participant's parent/caregiver (10 min).

xi. The Vineland Adaptive Behavior Scales (VABS): ICF D

The VABS is a widely used informant report checklist that will be used to assess four domains: communication; self-care; social skills; and maladaptive behavior. It will be completed by the participant's parent/caregiver (30 min).

xii. Childhood Autism Rating Scale, Second Edition (CARS-2): ICF D

An examiner completed behavioral rating scale used to evaluate symptoms of autism following a direct observation of a child. The parent-child structured interaction will be used as the context which is evaluated for this measure.

xiii. The Aberrant Behavior Checklist (ABC): ICF A, B, and D

A behavior rating scale completed by the parent/caregiver that is frequently used to examine treatment effects on challenging behaviors for individuals with FXS. The scale is comprised of 58-items in the following domains: (1) irritability, agitation, crying; (2) lethargy, social withdrawal; (3) stereotypic behavior (4) hyperactivity, noncompliance; and (5) inappropriate speech (15 min). The Sansone et al. (2011) FXS-normed ABC scoring measures will be used. The social avoidance subscale score will be a secondary clinical endpoint.

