i. The Clinical Global Impressions Scale–Severity (CGI-S) and Improvement (CGI-I) (Busner & Targum, 2007): ICF B

These standardized assessment instruments are widely used in drug trials to enable the clinician to utilize history from the parents or caregiver and incorporate it into a clinical rating, first for severity, and then for clinical follow-up. The CGI-S will be used at the pre-treatment assessment to judge symptom severity and the CGI- I will be used at the 3 month and 6 month visits.

ii. The Visual Analogue Scale (VAS): ICF B

The measure will be used to assess parental impressions of progress in two key symptoms: spoken language impairment and social impairment. The distance of the mark from one end is used as the outcome variable for analysis. The VAS will be administered at each visit. The VAS has been effectively used as an outcome measure in other FXS drug trials (Erickson et al., 2011; Paribello et al., 2010; [name] et al 2013).

11 (b). Medical/Safety Assessments (Consent Form B):

The schedule of procedures is also listed in a table format below:

Assessment	Screening/Baseline Visit 1 (Week 1, Day 0)	Visit 2 (Week 10 ± 3 Days)	Visit 3 (Week 20 ± 3 Days)	
Informed Consent	X			
Inclusion/Exclusion Criteria	X			
Medical History	X			
Vital Signs	X	X	X	
Physical Exam	X	X	X	
Neurological Exam	X	X	X	

For IRB Use

Document Revision Date: July 12, 2013

Concomitant Medications	X	X	X
Adverse Events	X	X	X
Clinical Labs	X	X	X
Biomarkers	X	X	X
Leiter-R (45 min.)	X		
ADOS-2 (45 min.)	X		
CGI-S	X		
CGI-I		X	X
VAS	X	X	X
Language Assessments			
CELF-4 (15 min.)	X		X
CASL (45 min.)	X		X
TROG-2 (10 min.)	X		X
PPVT-4 (10 min.)	X		X
EVT-2 (10 min.)	X		X
FACB (45 min.)	X		
Child Spoken Language (30 min.)	X		X
Parent Narrative Task 1 (15 min.)	X		X
Parent Narrative Task 2 (15 min.)	X		X
Parental Assessments			
K-BIT-2 (maternal) (25 min.)	X		
Parent Questionnaires			
ABC (15 min.)	X	X	X
ADAMS (10 min.)	X	X	X
RBS-R (10 min.)	X	X	X
PSI (10 min.)	X		X
PSOC (10 min.)	X		X
Family Background	X		
Questionnaire (10 min.)			
SCL-90 (maternal) (10 min.)	X		X
Post Treatment Survey			X
Dispense Medication	X	X	

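### Aim 2, treatment-response branch: markers are related to an undefined response group although the primary outcome is continuous, and cutting that outcome would lose at least 36% of the information

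*Combined protocol and SAP*

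**What the plan says.** Section 10, Aim 2, covers all three biomarker hypotheses with one model: "In the addressing hypotheses 2a, b, and c, we will identify biomarkers associated with FXS using a regression model for marker expression". Its predictor is a class variable, the model being specified "with grouping of phenotype (i.e., disease state or respond to treatment) as a predictor with important clinical cofounders as covariates". The next step is classification: "The marker performance will be evaluated using receiver operating characteristic (ROC) curves", for both diagnostic and prognostic use, followed by predictive signatures from PAM or a similar method.

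Hypothesis 2c (section 3, Objectives) is the one that concerns who benefits: "Individuals with elevated inflammatory cytokines will be more responsive to lovastatin".

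The trial's main outcome is not a class. Section 10 states: "The primary outcome measure is a spoken language composite measured at baseline and at the end of treatment". Section 11(a), Child Spoken Language, builds it by "taking a weighted mean of variables reflecting talkativeness, fluency, intelligibility, vocabulary diversity, and syntactic complexity".

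No section says which measure defines response, where the cut lies, or what share of children should count as responders.

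**The concern.** Three features of the response branch fit poorly with its purpose.

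- **Grouping.** Turning a continuous score into two classes treats a child just above the cut like one far above it. In a trial of 50 children that costs power the trial can ill afford.
- **Open cut.** Section 10 lists about a dozen candidate markers. With no response measure or cut stated, both could be settled after the data are seen, and the markers that look predictive could depend on that choice.
- **Form of the model.** The marker is the dependent variable and response the predictor. Hypothesis 2c runs the other way, and it is about response to lovastatin in particular. Every child in Phase 3 receives PILI, so improvement in a lovastatin-treated child mixes the effects of drug, PILI and time. A responder label cannot separate these; a comparison of marker slopes between arms can.

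The plan already has a better form nearby. For Hypothesis 1b it regresses the 20-week composite on treatment, parent behavior and their interaction, adjusted for baseline. For child moderators of response to lovastatin it uses linear regression. No reason is given for handling biomarkers differently.

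**Working it through.** **Plan's own figure.** There is none for Aim 2. The only numerical power statement, 80% at effect size 0.6, concerns the primary two-group comparison and is not used here.

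**Inputs from the documents.** N = 50 in Phase 3 (section 4); half randomized to lovastatin, so about 25 (section 17); two-sided alpha 0.05 (section 10); a composite that is a weighted mean (section 11(a)).

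**Assumptions, not in the documents.** Response is taken from the composite; the score is normally distributed; the responder share p is 0.5, 0.3 or 0.2; the marker-outcome correlation is 0.3, 0.4 or 0.5.

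**Step 1: information kept.** For a normal score cut so that a share p are responders, with c the matching normal quantile and φ the normal density, efficiency = φ(c)² / [p(1 − p)].

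- p = 0.5: 0.3989² / 0.25 = 0.637, a loss of 36%. Fifty children count as 31.8, and 25 as 15.9.
- p = 0.3: 0.3477² / 0.21 = 0.576, a loss of 42%. Fifty count as 28.8, and 25 as 14.4.
- p = 0.2: 0.2800² / 0.16 = 0.490, a loss of 51%. Fifty count as 24.5, and 25 as 12.2.

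The median split is the best case for any two-group cut of a normal score.

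**Step 2: power.** The correlation shrinks by the square root of the efficiency (0.798, 0.759, 0.700). A correlation of 0.4 becomes 0.319, 0.304 or 0.280. Simulated power (20,000 runs, no covariates, no multiplicity adjustment):

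| Children | Correlation | Continuous | 50/50 | 30/70 | 20/80 |
|---|---|---|---|---|---|
| 50 | 0.3 | 57% | 39% | 35% | 30% |
| 50 | 0.4 | 84% | 64% | 58% | 51% |
| 50 | 0.5 | 97% | 84% | 80% | 72% |
| 25 | 0.3 | 31% | 20% | 19% | 16% |
| 25 | 0.4 | 53% | 34% | 30% | 26% |
| 25 | 0.5 | 75% | 52% | 46% | 40% |

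The Fisher approximation, Φ(atanh(r)·√(n − 3) − 1.96), agrees. At r = 0.4 it gives 83%, 62%, 57% and 50% with 50 children, and 51%, 34%, 31% and 27% with 25. Differences of one or two points from the table reflect simulation error, the approximation and rounding of group sizes.

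**Step 3: what the interaction costs.** With marker and outcome in SD units, suppose the slope is 0.4 on lovastatin and 0 on placebo. The residual variances are then 1 − 0.16 = 0.84 and 1. The standard error of the slope difference is √(0.84/25 + 1/25) = 0.271, so 0.4 / 0.271 = 1.47 and power is Φ(1.47 − 1.96), about 31%. Using the t distribution lowers this slightly. The table describes a single marker-response association, so it must not be read as the power of the 2c test.

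**The case against.** The best reply is that the plan never says the composite will be cut. Response might come from the CGI-I, an ordinal clinician rating, or from the VAS (both exploratory measures in section 11(a)). Section 11(b) also speaks of correlating monocyte calcium responses with treatment response, which could be continuous. This stands, and it is why every loss figure here is conditional. It does not remove the point. Section 10 analyses CGI and VAS by the same approach as the primary outcome, not by responder class, and the calcium text gives no scale for response. On any of these readings, response remains undefined.

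Two stronger readings are tempting. A reader might infer that the plan discards a third of the information in its 50-child sample. The documents do not support that as a fact about the plan: it needs the composite, a median split and normality. For response to lovastatin, the relevant base is also nearer 25 children. A reader might also infer that every marker test loses power. That is wrong. Disease state is a natural category, and Hypotheses 2a and 2b concern lovastatin's effect on signalling, for which section 11(b) compares baseline with treatment samples.

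It can also be said that the reversed direction does not matter, because an unadjusted two-variable association is symmetric and ROC and PAM address prediction. The first part is right: the power loss above does not come from the direction. But the direction does keep baseline composite and a marker-by-arm term out of an outcome model, and 2c needs that term.

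**Conclusion.** The point holds for the treatment-response branch of Aim 2, chiefly Hypothesis 2c. The plan relates markers to a response class that it does not define, when a continuous outcome and a suitable model form are already in the same section.

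If the composite supplies the class, the loss is 36% at best and 42% to 51% for 30/70 to 20/80 splits. At an assumed correlation of 0.4, that is about 20 to 25 points of power with 50 children for a median or 30/70 split, and about 19 to 22 points with 25. These figures rest on normality, on the assumed correlation and splits, and on unadjusted tests of one marker at a time.

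The primary and secondary endpoint analyses are untouched. The change is worth making but is not critical to the trial's main result.

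**What to change.** For the treatment-response questions, replace the grouped regression in section 10 with:

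Week 20 composite = baseline composite + arm + baseline marker + marker × arm.

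Name the interaction as the test of Hypothesis 2c. The marker main effect without it would be only prognostic: a marker with the same slope in both arms would look positive while saying nothing about lovastatin.

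Keep ROC curves and PAM signatures as descriptive supplements. State which measure defines response and what the cut is, and fix both before unblinding. Leave the disease-state and pre/post signalling analyses as they are.

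No new data are needed: the schedule in section 11(b) already collects biomarkers at all three visits and the language samples at baseline and Week 20. The cost is a paragraph of plan text and a little more analysis. The real downside is that the interaction test is weak at N = 50 (about 31% in the example worked above, before any multiplicity adjustment). The plan should say so and report the interaction estimate with its confidence interval, so that a null result is not read as evidence against 2c.

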pathways/proteins influenced by FMRP (the mitogen-activated protein kinase (ERK) and MMP-9) are biomarkers of treatment responsiveness. Because lovastatin is also an anti-inflammatory, we will characterize MEK/ERK signaling in peripheral immune cells both and pre- and post- treatment to determine whether levels of these signaling molecules are predictive biomarkers of treatment response. We hypothesize that those individuals with elevated inflammatory cytokine profiles will be most responsive to lovastatin treatment. Once modeled in FXS, results from these studies can then be applied to other neurodevelopmental disorders including Rasopathies.

Lovastatin as a treatment for FXS: Lovastatin is an inhibitor of the rate-limiting enzyme in cholesterol biosynthesis and an FDA-approved treatment for hyperlipidemia. Lovastatin has also been proposed as a treatment for IDD, particularly for Rasopathies and Neurofibromatosis Type 1 (NF1). Lovastatin reduces activation of the small guanosine triphophatase (GTPase) Ras, which in turn reduces activity of the MEK/ERK signaling pathway. Lovastatin interferes with recruitment of Ras to the membrane, a process required to transition from inactive GDP to active GTP. The interaction of Ras with the membrane requires the prost-translational addition of a farnesyl group to the C terminus of Ras, and lovastatin inhibits Ras farnesylation by targeting the upstream mevalonate pathway.

Recent extensions of animal studies to FXS have been promising. In a study of Fmr1 knock out (KO) mouse, intraperitoneal injections of lovastatin protected the mice from audiogenic seizures that are part of the FXS phenotype. In the KO mouse, the lack of FMRP represents a loss of the translational repressor for many proteins important for synaptic plasticity. Lovastatin corrected the excessive protein production in the KO mouse, inhibited RAS-ERK1/2 signaling in hippocampal neurons, and improved the phenotype. Although lovastatin has been used to treat children as young as one year of age, FDA approval extends only to 10- to 17-years-olds and studies of efficacy for cognitive impairments in NF1 have shown benefit and safety for this age range so this study will focus on the same age group.

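### Aim 2 plans a diagnostic analysis with no non-FXS sample described, and its one stated regression does not test Hypothesis 2c

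*Combined protocol and SAP*

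**What the plan says.** Section 3 (Objectives), Aim 2(a), sets out to "Identify biomarkers in peripheral immune cells associated with FXS and the efficacy of treatment". Hypothesis 2c in the same section reads "Individuals with elevated inflammatory cytokines will be more responsive to lovastatin", and section 4 (Background) repeats the idea: "We hypothesize that those individuals with elevated inflammatory cytokine profiles will be most responsive to lovastatin treatment".

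Section 10 (Study Endpoints) gives one analysis paragraph for Hypotheses 2a, 2b and 2c together:

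- The investigators will "identify biomarkers associated with FXS using a regression model for marker expression with grouping of phenotype (i.e., disease state or respond to treatment", with clinical confounders as covariates.
- Marker performance will be judged by "receiver operating characteristic (ROC) curves to test which biomarkers are statistically better diagnostic and prognostic tests for FXS".
- PAM or a similar method will then build signatures of MEK/ERK and Rho GTPase elements in response to lovastatin.

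The candidate markers are several phosphorylated signalling proteins and "levels of IL-1, IL-6, IL- 10, MCP-1, IL-1alpha, IL-1beta, MMP-9, and MIF".

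Two other statements in section 10 serve as a contrast. For Hypothesis 1b, "The regression will include main effect terms for both treatment and parent behavior as well as the interaction term". For response to the drug more generally, "Additional analyses will examine potential child moderators of response to lovastatin (age, Leiter, ADOS symptom severity) using linear regression".

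**The concern.** There are two separate problems.

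**Comparator.** A diagnostic ROC curve and a disease-state coefficient both need people with and without FXS. If only children with FXS give biomarker blood, that half of the analysis cannot be produced, and the part of Aim 2(a) about association with FXS has no data behind it.

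**Hypothesis 2c.** Being more responsive to lovastatin is a claim about how the drug-placebo difference changes with the marker. A comparison of marker levels between responders and non-responders answers a different question: whether the marker goes with improvement. Section 17 (Potential Benefits to Subjects) says that all trial participants receive PILI, so children can improve without the drug. A marker of general improvement could then be published as a predictor of lovastatin benefit.

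**Working it through.** **1. Is there a non-FXS biomarker sample?**

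Section 6 (Number of Subjects) gives 30 (Form A) + 50 (Form B) + 30 (Form C) + 3 (Form D) = 113. This reproduces the stated total, so no further enrolled group is left over. Going through the possible sources:

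- *Form B trial.* Biomarker blood, about 30 ml at each of three visits, is described in section 11(b), which is headed for Consent Form B. Inclusion criterion 1 (section 5) requires a full mutation. Non-FXS children: 0.
- *Form C pilots.* Some have Down syndrome or autism, but section 11 describes a single visit for picture-book interaction with a clinician and no blood draw.
- *Control plasma.* Section 11(b) uses it to normalise between assay plates.
- *Laboratory members' cells.* Section 11(b) uses them to optimise assays.
- *Antigen-presenting cell assays.* The comparison stated in section 11(b) is baseline against treatment samples in children with FXS.

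With 0 non-FXS samples, disease state takes one value. Its regression coefficient, the specificity and the AUC cannot be estimated. The response regression and a response ROC need only the 50 trial children and remain possible.

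**2. Does any stated analysis test Hypothesis 2c?**

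| Stated analysis (section 10) | Compares the drug effect across cytokine levels? |
|---|---|
| Marker on disease state or response | No; no arm-by-marker term |
| PAM signatures | No; concerns MEK/ERK and Rho GTPase elements, no placebo contrast stated |
| Moderators: age, Leiter, ADOS severity | No cytokine listed |
| Hypothesis 1b interaction | Arm by parent behaviour only |

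The plan does not define response, does not say whether responders come from both arms or from lovastatin only, and gives no cut-off for elevated cytokines.

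**3. How far could a responder comparison mislead?**

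From the documents: 50 children, half to lovastatin (25 per arm), and the 0.6 SD effect of the power statement. Assumed, and not in the documents: response is above-median change, the marker-outcome correlation ρ is equal in both arms (no true modification), and tests are at 0.05.

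Model: change = 0.6 × arm + ρ × marker + √(1 − ρ²) × error. Simulated share of trials with p < 0.05 (repeat runs agree to about one point):

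| ρ | Responder test, arms pooled | Responder test, lovastatin only | Arm × marker |
|---|---|---|---|
| 0.1 | 8% | 7% | 5% |
| 0.3 | 36% | 21% | 5% |
| 0.5 | 80% | 52% | 5% |

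Adding arm as a covariate to the pooled comparison does not help (8%, 36% and 82%).

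With a true modifier (slope 0 on placebo, 0.6 on lovastatin, residual SD 1), power is about 28% pooled, 54% lovastatin-only and 50% for the interaction.

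**4. Power of the interaction test**

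Take a 50:50 marker split and 50 complete cases, so four cells of 12.5. In units of residual SD after baseline adjustment, SE = √(4/12.5) = 0.566. With 45 df the critical t is 2.014, so the 95% CI half-width is 2.014 × 0.566 = 1.14 SD. By the noncentral t, power is 18% for a 0.6 SD interaction and 41% for 1.0 SD; 80% needs about 1.6 SD. With 40 complete cases, SE = √(4/10) = 0.632 and power is 15% and 34%.

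**5. Multiplicity**

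Eight analytes each tested at 0.05 give 1 − 0.95⁸ = 34% chance of at least one false positive if independent, and about 20% in simulation at inter-analyte correlation 0.7. Testing one analyte at 0.05 and separately Holm-adjusting the other seven is not enough: 1 − 0.95 × (1 − 0.05/7)⁷ = 9.6% if independent, and about 7–8% in simulation at correlation 0.5–0.7.

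**The case against.** The best defence is that section 10 covers three hypotheses in one short paragraph and is brief throughout; even the age, Leiter and ADOS moderator analysis writes out no interaction term. On this view the plan is silent about 2c, and it never commits to judging 2c on a responder contrast that ignores arm. It is true that the harm depends on how the analyst fills the gap. But the regression is stated expressly for 2c, none of the ways of defining responders considered above turns it into a test of effect modification, and the authors did write an interaction for Hypothesis 1b.

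Second, only part of the plan fails on the comparator. The text offers disease state or response, and diagnostic and prognostic use. This stands: a reader might infer that Aim 2 as a whole cannot be run, and the documents do not support that. Nor do they show that no suitable non-FXS sample exists anywhere; they only describe none.

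Third, the false-positive figures rest on an assumed correlation and responder definition. The CGI-I is also collected and could define response instead. This stands too: at a correlation of 0.1 the excess is only 2–3 points. The 34% multiplicity figure likewise treats all eight analytes as independent tests of 2c, although 2c concerns inflammatory cytokines and the list includes MMP-9 and overlapping IL-1 entries.

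Finally, the interaction test is weak at this sample size. That is correct and is stated below as a cost.

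**Conclusion.** Wrong as written, on two counts. The disease-state predictor and the diagnostic ROC cannot be estimated from the samples described; this follows from the text and needs no assumption. The regression stated for Hypothesis 2c does not test it; this also follows from the text.

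Only the size of the second problem is assumption-bound: roughly 7–8% false claims of a lovastatin marker at a marker-outcome correlation of 0.1, rising to 52% (lovastatin only) or 80% (pooled) at 0.5, against 5% for the interaction.

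A reader might infer that the responder comparison also misses true modifiers. The calculation does not support that in general: in the example the lovastatin-only comparison has 54% power and the interaction 50%. The interaction test gains specificity, not power. A reader might also infer that the trial's main result is compromised. It is not: Aim 2 feeds neither the spoken language composite nor the social avoidance endpoint. The point still merits correction before unblinding, because Aim 2 is one of two stated aims and its blood is drawn from children at three visits.

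**What to change.** **Comparator.** In the Aim 2 paragraph of section 10, delete *disease state* and *diagnostic*, and limit Aim 2(a) in section 3 to biomarkers of treatment response within FXS. Alternatively, name an already available non-FXS sample and say how it is matched. Deleting gives up the diagnostic part of a stated objective.

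**Hypothesis 2c.** Add to section 10:

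> Exploratory analysis for Hypothesis 2c: in all randomised children with a baseline cytokine value and a week-20 spoken language composite, the week-20 composite will be analysed by ANCOVA on baseline composite, assigned arm, baseline log cytokine and arm × cytokine. The interaction estimate will be reported with its 95% confidence interval, and the number of children missing either value will be reported by arm. One primary cytokine will be named before unblinding and tested at 0.05. The other analytes will be reported as estimates with confidence intervals and without significance claims.

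If tests of the other analytes are wanted, apply Holm to them only when the primary cytokine is significant; testing the two families separately gives about 7–10% family-wise error. The continuous log value avoids inventing a cut-off for elevated, and section 11(b) already plans the log transformation. The missing-data wording is needed because section 11(a) lets procedures unsuited to a child be skipped, and section 15 allows discontinuation.

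**Cost.** No new visits, blood or participants. The test is weak: at a 50:50 split, about 18% power for a 0.6 SD interaction and 41% for 1.0 SD with 50 complete cases (15% and 34% with 40). Hence the exploratory label and the emphasis on the interval.
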